2.2. Timings of Analyses

The primary analysis of safety, tolerability, efficacy and/or pharmacokinetics is planned after all subjects complete the final study visit or terminate early from the study, the database is locked, evaluability decisions are made, and the treatment identifiers unblinded.

An independent Data and Safety Monitoring Board (DSMB), or otherwise called Independent Data Monitoring Committee (IDMC), will review accumulating safety data periodically during the study. An independent unmasked team from biostatistics will perform the analyses to maintain the masking of the study. Analyses for the DSMB are described in a separate DSMB SAP.

An interim analysis (IA) is planned when approximately 84 randomized subjects have completed Week 8 of the study. The results of the IA will be used, by designated AnaptysBio personnel (employees and/or consultants) without direct contact with the sites, to make decisions for a Phase 3 program and determine the likelihood for further etokimab clinical development in other indications. An unblinded team from

biostatistics will perform the analyses as described in Section 3.7 of this SAP (refer to blinding tain the blinding of the study).

3. STUDY OBJECTIVES

3.1. Primary Objective

To evaluate the efficacy of etokimab compared to placebo in the treatment of subjects with CRSwNP following a 16-week treatment period (change from baseline using co-primary endpoints).

3.2. Secondary Objective(s)

To evaluate:

- Effectiveness of etokimab compared to placebo in subjects with CRSwNP in relieving clinical symptoms.
- Safety and tolerability of etokimab in subjects with CRSwNP compared to placebo following a 16-week treatment period.
- Pharmacokinetics (PK) of etokimab in human serum in subjects with CRSwNP following subcutaneous (SC) administration.

3.3. Exploratory Objective(s)

To evaluate:

- Improvement in Quality of Life (QoL) in subjects with CRSwNP treated with etokimab compared to placebo following a 16-week treatment period.
- Other effects of etokimab compared to placebo in subjects with CRSwNP following a 16-week treatment period.

3.4. Brief Description

The current study, ANB020-006, is a randomized, double blind, placebo controlled, parallel group, multiple dose, Phase 2 study designed to assess efficacy, safety, tolerability, and PK of two different doses and dose regimens of etokimab following a 16-week treatment period compared to placebo in adults with moderate to severe CRSwNP.

This study has 3 periods: a 4-week screening period (maximum of 31 days), with a minimum MFNS run-in of 20 days prior to the administration of study medication on Day 1; a 16-week treatment period (Week 0 to Week 16); and an 8-week safety follow-up period. The total participant duration will be approximately 28 weeks.

During the screening period, all subjects will undergo evaluation for eligibility. Randomization will be stratified by a subject's asthma comorbidity: yes/no. The subjects will be randomly assigned on Day 1 to 1 of the following 3 treatment arms in a 1:1:1 ratio:

- Etokimab 300 mg load + 150 mg SC every 4 weeks (Weeks 0, 4, 8, and 12)
- Etokimab 300 mg load + 150 mg SC every 8 weeks (Weeks 0 and 8) and placebo (Weeks 4 and 12)
- Placebo (Weeks 0, 4, 8, and 12)

Eligible subjects will be administered study medication SC during onsite visits on Day 1 (Week 0), Day 29 (Week 4), Day 57 (Week 8), and Day 85 (Week 12). Subjects will remain onsite for 2 hours for post dose observation following each study medication injection. Additional visits will occur on Day 5 (Week 1) and Day 113 (Week 16) during the treatment period. During the safety follow up period, subjects will return to the study center on Day 141 (Week 20) and Day 169 (Week 24)/end of study (EOS).

3.5. Subject Selection

Eligibility for study participation is based on the inclusion and exclusion criteria in the following sections.

3.5.1. Inclusion Criteria

Subjects must meet all of the following criteria in order to be eligible to participate in this study:

- 1. Male or female, aged 18 to 70 years at the time of consent.
- 2. Present with a minimum bilateral total nasal polyp score of 4 out of 8 (maximum score), with minimum of 1 in each nostril, despite completion of a prior intranasal corticosteroid (INCS) treatment for at least 8 weeks before screening.
- 3. Present with at least 2 of the following symptoms prior to screening:
 - a. Nasal blockade/obstruction
 - b. Nasal congestion
 - c. Nasal discharge (anterior/posterior nasal drip)
 - d. Facial pain/pressure, and
 - e. Reduction in or loss of smell.
- 4. Body mass index (BMI) of 18 to 42 kg/m² (inclusive) and total body weight > 50 kg (110 lb).
- 5. Agrees to the following conditions regarding contraception and pregnancy:
 - a. A male subject must agree to use contraception as detailed in the protocol during the treatment period and for at least 3 months after the last dose of study treatment and refrain from donating sperm during this period.
 - b. A female subject of child bearing potential must have a negative serum pregnancy test (β -human chorionic gonadotropin) at screening and a negative urine pregnancy test at baseline (Day 1), is not lactating, and at least one of the following conditions applies:
 - i. Not a woman of childbearing potential (WOCBP) as defined in the protocol OR
 - ii. A WOCBP who agrees to follow the contraceptive guidance in the protocol during the treatment period and for at least 3 months after receiving the last dose of study treatment. The female subject's selected form of contraception must be effective by the time the female subject enters into the study (e.g., hormonal contraception should be initiated at least 28 days before Study Day 1).
- 6. Screening laboratory values must meet the following criteria:
 - a. AST and ALT levels $\leq 3 \times ULN$
 - b. Total Bilirubin $\leq 1.5 \text{ x ULN}$

c. Albumin \ge 3 g/dL - Lipase \le 1.5 ULN (if collected)

If a subject has liver function tests (LFTs) within normal and defined limits at screening and meets all other inclusion criteria at screening and baseline, the subject can be dosed.

- 7. Capable of giving signed informed consent and understanding the requirements and restrictions listed in the informed consent form (ICF).
- 8. Subject must use mometasone furoate nasal spray (MFNS) as provided by the Sponsor and be approximately 80% compliant during the screening period through Day 1.
- 9. Willing to and capable of complying with the study protocol requirements.
- 10. Able to read and to understand the study procedures and have the ability to communicate meaningfully with the investigator and staff.
- 11. Confirmation of completion of 1 week of daily NPIF recordings (twice daily) on Day 1, prior to randomization. (A minimum of approximately 5 days must be completed of the 7 consecutive days requested).

3.5.2. Exclusion Criteria

Subjects are excluded from the study if any of the following criteria apply:

- 1. Prior exposure to etokimab.
- 2. SNOT-22 score \leq 15 at screening.
- 3. Use of other investigational drugs or prohibited therapy for this study within 8 weeks before Screening or 5 half-lives, whichever is longer:
 - a) Have required an increase of oral corticosteroids (OCS) or INCS drops within the 2 months before screening or are scheduled to receive OCS during the study period for another condition.
 - b) Have undergone any previous monoclonal antibody (mAb) or immunosuppressive treatment.
 - c) Leukotriene antagonists/modifiers for subjects who were not on a continuous treatment for \geq 30 days prior to screening.
- 4. Have a documented history of aspirin-exacerbated respiratory disease (AERD) diagnosis as confirmed by a medical provider with an oral aspirin challenge.
- 5. Have concomitant medical condition(s) that may interfere with the investigator's ability to evaluate the subject's response to the investigational product (IP).
- 6. Have experienced a severe life-threatening anaphylactic reaction to human, humanized, chimeric, or murine monoclonal antibodies.
- 7. Have participated in any interventional study for the treatment of CRSwNP in the 3 months before screening.
- 8. Have received high dose systemic corticosteroids (equivalent to > 15 mg/day prednisone), prolonged nonsteroidal, immunosuppressant, or immunomodulating treatments within 8 weeks before screening.
- 9. Have received treatment with biologics such as dupilumab, mepolizumab, or omalizumab within 12 weeks or 5 half-lives (5 $T_{1/2}$), whichever is longer, before screening.

- 10. Clinically significant abnormal ECG assessment at screening (any abnormality that the investigator believes is not safe for study participation).
- 11. History of ischemic cardiovascular disease(s) or cerebrovascular event within 1 year of screening.
- 12. Have received any systemic antibiotic treatment within 4 weeks before screening.
- 13. Have a history of hypersensitivity or allergic reactions to polysorbate 80, a component of the etokimab formulation or the inactive ingredients (excipients).
- 14. If female, is pregnant or lactating, or intends to become pregnant during the study period.
- 15. Current smokers or former smokers with a smoking history of ≥ 10 pack-years [(number of cigarettes per day/20) × number of years smoked]. A former smoker is defined as a subject who quit smoking at least 2 months prior to Screening visit. This includes electronic cigarettes and vaping. Subjects who smoke medicinal marijuana can be enrolled at the investigator's discretion (conversion to edible forms of marijuana is preferred). Occasional smoking is permitted at the discretion of the investigator (e.g., cigar or pipe for significant event, occasional/rare weekend cigarette or marijuana use).
- 16. Positive blood screen for hepatitis C virus antibody, hepatitis B virus core antibody, hepatitis B surface antigen, or human immunodeficiency virus (HIV) 1 and 2 antibodies (except subjects who test positive for hepatitis B surface antigen alone due to a hepatitis B vaccination).
- 17. Presence of chronic or active infection at screening including positive result for active tuberculosis (TB) (i.e. positive QuantiFERON® test result without any prior history of active nor latent TB infection and without evidence of active infection) where the subject has not completed prophylactic treatment.
- 18. Any co-morbidity that the investigator believes is a contraindication to study participation. This includes, but is not limited to, any respiratory (e.g., pulmonary fibrosis, eosinophilic granulomatosis with polyangiitis, allergic bronchopulmonary aspergillosis), cardiovascular, gastrointestinal, hematological, neurological, immunological, musculoskeletal, renal, infectious, neoplastic, or inflammatory condition that may place the safety of the subject at risk during the study, impact results of the study or their interpretation, or prevent subject from completing the study.
- 19. Comorbid asthma when:
 - a) Forced expiratory volume (FEV₁) \leq 60% of predicted normal as assessed on Day 1 and defined by the Global Lung Initiative (GLI)
 - b) An exacerbation requiring systemic (oral and/or parenteral) corticosteroid treatment or hospitalization (> 24 hours) for treatment of asthma within 3 months prior to screening.
 - c) A daily dose higher than 1000 µg fluticasone or the equivalent of inhaled corticosteroids.
- 20. Have any other physical, mental, or medical condition that, in the opinion of the investigator, makes study participation inadvisable or could confound study assessments.
- 21. Receipt of live attenuated vaccine within 4 weeks before screening.
- 22. Planned surgery during the study or 30 days before screening.
- 23. History of malignancy within 5 years, except non-melanoma skin cancer that has been fully treated with no current active disease.
- 24. Initiation of allergen immunotherapy:
 - a) Within 12 weeks prior to screening

- b) Planned to begin therapy during the screening period
- c) Planned to begin during the randomized treatment period.

Subjects who started immunotherapy more than 12 weeks prior to screening can continue the immunotherapy during the study providing dosing is at least 2 weeks prior to each dose of study drug.

- 25. Undergone any nasal surgery (e.g. any procedure with excision of tissue) within 3 months before randomization (Day 1).
- 26. Evidence of drug/substance abuse that would pose a risk to subject safety, interfere with the conduct of the study, or affect the subject's ability to participate in or comply with the study protocol, including but not limited to evidence of misuse of addictive drugs, such as opioids, outside of prescribed medications for a medical condition.

3.6. Determination of Sample Size

The two co-primary endpoints were assessed in order to determine the sample size that will provide adequate power to detect a clinically meaningful difference between each etokimab dosing regimen and placebo.

Sample size estimates were calculated based on the following assumptions:

- Overall alpha=0.05
- Co-primary endpoints
- Hierarchical testing of the 2 active treatment arms versus placebo

Based on data from similar trials conducted in adult subjects with CRSwNP, a difference in NPS of 1.3 between the etokimab change from baseline to week 16 and the placebo group change from baseline to week 16 will be clinically meaningful (*Bachert et al. 2016*). Assuming a standard deviation of 1.5, and a significance level of 5%, a sample size of n=27 for each treatment arm will provide approximately 87% power to detect the stipulated difference. In order to account for the dilution of treatment effect due to 18% dropouts and missing data, approximately 33 subjects are planned to be randomized equally to each of the three treatment arms.

The second co-primary endpoint is SNOT-22 total score. In a trial of adults with CRSwNP, the difference in mean change from baseline to Week 16 between active and placebo was 18.1. Assuming a common standard deviation of 19.2, and 2-sided significance level of 5%, the sample size of 27 subjects provides 92% power to detect the stipulated treatment difference. Hence, adjusting for 18% dropouts and missing data, n=33 subjects will provide >85% desired power to detect a clinically meaningful difference in this endpoint between each active arm and placebo.

Each co-primary endpoint will will be tested against two-sided alpha=0.05; therefore, the combined power for the testing of both endpoints is approximately 80%, assuming no negative correlation between endpoints.

3.7. Treatment Assignment & Blinding

Eligible subjects will be randomized on Day 1 to 1 of 3 treatment arms in a 1:1:1 ratio based on a computergenerated centralized randomization schedule prepared under the supervision of the sponsor.

• Arm 1 (Eto Q8W): Etokimab 300 mg load + 150 mg SC every 4 weeks (Weeks 0, 4, 8, and 12)

- Arm 2 (Eto Q4W): Etokimab 300 mg load + 150 mg SC every 8 weeks (Weeks 0 and 8) and placebo (Weeks 4 and 12)
- Arm 3 (Placebo): (Weeks 0, 4, 8, and 12)

The randomization will be stratified by asthma comorbidity. The IXRS will assign a unique treatment code, which will dictate the treatment assignment and matching study medication kit for the subject. The pharmacist or designee will not be aware of treatment assignment (etokimab or placebo) and will be provided only kit numbers to assign study medication.

Study medication is provided as etokimab or matching placebo for SC injection:

- Sterile etokimab in single-use glass vials; each vial will contain 100 mg/mL of etokimab.
- Sterile placebo in identically matched single-use glass vials; each vial will contain no active drug product

All calls resulting in an unblinding event are recorded and reported by the IXRS. If a subject's treatment assignment is unblinded, the sponsor must be notified within 24 hours after breaking the blind without informing the sponsor of the treatment assignment. The date and reason that the blind was broken, but not the treatment assignment, must be recorded in the source documentation and electronic case report form (eCRF), as applicable.

An unblinded statistician and statistical programmer separate from the study team will be responsible for providing unblinded reports to the DSMB, for presentation of the unblinded reports for the formal interim analysis, and for handling unblinded PK and other data (e.g. eosinophils) that may potentially unblind the study. Data import agreements will provide for protections from revelation of unblinded subject information.

[figure not shown]
maintains a restricted area within its programming environment that will not be accessed el associated with routine handling of study information.

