2. PURPOSE

The purpose of this statistical analysis plan (SAP) is to describe the statistical analyses that will be performed and to ensure that data listings, summary tables and figures which will be produced, and the statistical methodology that will be used, are prespecified, complete and appropriate to allow valid conclusions regarding the study objectives. This version of the SAP is based on Amendment 3 of the Protocol, dated 06 February 2020.

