6. GENERAL ASPECTS FOR STATISTICAL ANALYSIS

6.1. General Methods

The following conventions will be utilized in the analyses:

- The final statistical analysis will not be performed until all the reportable data have been collected, queries answered, and the database locked.
- All relevant individual subject data will be provided in data listings sorted by treatment arm and subject number. The following treatment group labels will be used: "Placebo", "etokimab Q8W", and "etokimab Q4W". Where subjects who were not randomized are included in listings, the treatment arm will be indicated as "Not Assigned" or "Not Randomized".
- Tabulations will be produced for appropriate demographic, baseline, efficacy and safety parameters. All tabular summaries will be presented by treatment arm as indicated above. A total column may be included under "All Subjects" where necessary or appropriate.
- In general, continuous variables will be summarized by descriptive statistics including the number of observations (n), mean, standard deviation (SD) or standard error (SE), median, minimum (min), and maximum (max); the lower (Q₁) and upper quartile (Q₃) may be included in some summaries if deemed necessary or important. The same number of decimal places as the raw data will be presented when reporting min and max, 1 more decimal place than in the raw data will be presented when reporting mean, median, lower and upper quartiles and 2 more decimal places than in the raw data will be presented when reporting SD or SE.
- Categorical data will be summarized using the number of observations (n), frequency, and percentage of subjects in the relevant analysis set and treatment group falling within each category.
- Unless otherwise specified, where there are multiple measurements at a post-baseline visit or time of assessment, the value closest to the target date within the specified window for the assessment visit will be used for analysis.
- For numerical variables, change from baseline will be calculated as the value of interest at the time of measurement minus the corresponding baseline value.
- All statistical tests will be two-sided; unless otherwise indicated; two-sided p-values < 0.05 will be regarded as statistically significant, and confidence intervals (CI) will be 2-sided and have 95% confidence level.
- All subject data will be included in listings.
- Data analyses will be conducted using validated computer software (e.g. SAS[®] Version 9.4 or higher).

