- Adverse events will be coded using the most recent MedDRA version 21.0 or higher.
- Concomitant medications will be coded using the most recent version of World Health Organization (WHO) -DDE version March 2018 or later.
- In this SAP, we will designate the treatment arms as Placebo, etokimab Q4W, and etokimab Q8W. In data presentations, etokimab Q4W will be in the 1st column, etokimab Q8W in the 2nd column, and the Placebo group in the 3rd column.

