8.1. Primary Efficacy Endpoint and Analysis

Statistical hypotheses associated with the co-primary efficacy endpoints are as follows:

- Treatment of adults diagnosed with CRSwNP using etokimab will result in a significantly greater reduction of Week 16 NPS from baseline when compared to placebo, and
- Treatment of adults diagnosed with CRSwNP using etokimab will result in a significantly greater reduction of Week 16 SNOT-22 score from baseline when compared to placebo

Statistical significance for the co-primary efficacy endpoints will be declared if and only if both 2-sided pvalues for the tests of the individual hypotheses are < 0.05. Testing will be conducted in a hierarchical manner for each co-primary endpoint such that the comparison of the etokimab Q4W treatment arm versus placebo will be conducted first. If the result from this test is statistically significant, then the comparison of the etokimab Q8W treatment arm versus placebo will be performed. If the result from the etokimab Q4W versus placebo is not statistically significant, no further testing will be performed for the etokimab Q8W treatment arm versus placebo.

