8.1.1.2. Primary Statistical Analysis for NPS

Statistical analysis of this endpoint will employ a general linear model with repeated measures (also called a mixed model with repeated measures, MMRM), with the change from baseline in NPS as the dependent variable; baseline (Day 1) NPS score as a covariate, treatment group (3 levels), stratification factor, treatment by stratification factor, categorical time points (Weeks 4, 8, 12 and 16) and treatment by time interaction as fixed effect factors, and subject as a random effect in the model. Assuming treatment (trtpn) is coded as Placebo=1, Eto Q8W=2, Eto Q4W=3, and that the time variable (weekn) is ordered as 4, 8, 12, and 16, we can write the SAS model of interest to be performed with SAS PROCEDURE MIXED as follows:

```
PROC MIXED DATA = DATASETNAME;
CLASS USUBJID WEEKN TRTPN STRAT;
MODEL CFB = BASE STRAT TRTPN STRAT*TRTPN WEEKN WEEKN*TRTPN / SOLUTION DDFM=KR;
REPEATED WEEKN / SUBJECT=USUBJID TYPE=UN;
LSMEANS WEEKN*TRTPN / CL ALPHA=0.05;
RUN;
```

The (co)primary hypothesis to be tested for this estimand is that treatment of adults diagnosed with CRSwNP using etokimab will result in a significantly greater reduction of Week 16 NPS from baseline when compared to placebo.

This hypothesis will be tested by comparing the least squares adjusted means for each etokimab dose group with placebo, at the week 16 time point. Comparison of each treatment arm with placebo will be based on the change in least squares means at Week 16 obtained from the MMRM. Testing will be conducted in a hierarchical manner such that the comparison of the etokimab Q4W treatment arm versus placebo will be conducted first.

If the results of the comparison of the eetokimab Q4W treatment arm versus placebo are statistically significant, the etokimab Q8W treatment arm will be compared to placebo.

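### SAP 3.7 swaps the two active-arm labels: the every-4-weeks regimen is called Eto Q8W and the every-8-weeks regimen Eto Q4W

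*SAP*

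**What the plan says.** SAP 3.7 (Treatment Assignment & Blinding) lists the arms as "Arm 1 (Eto Q8W): Etokimab 300 mg load + 150 mg SC every 4 weeks (Weeks 0, 4, 8, and 12") and "Arm 2 (Eto Q4W): Etokimab 300 mg load + 150 mg SC every 8 weeks (Weeks 0 and 8"), with placebo injections at Weeks 4 and 12 in the second of these.

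SAP 3.4 gives the same regimens in the same order but without short labels, starting with "Etokimab 300 mg load + 150 mg SC every 4 weeks (Weeks 0, 4, 8, and 12"). Protocol 4.1 and 6.1.2 do the same. The SAP glossary and Protocol 10.3 both expand Q4W as every 4 weeks and Q8W as every 8 weeks.

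From SAP 6.1 on, the active arms are identified by label only. That section fixes the group labels ("The following treatment group labels will be used") and the table layout ("etokimab Q4W will be in the 1st column, etokimab Q8W in the 2nd column"). SAP 8.1 sets the co-primary order: "the comparison of the etokimab Q4W treatment arm versus placebo will be conducted first". SAP 8.1.1.2 gives the model coding: "Assuming treatment (trtpn) is coded as Placebo=1, Eto Q8W=2, Eto Q4W=3". SAP 8.2 applies the same Q4W-then-Q8W order to the secondary endpoints, and SAP 8.2.2 repeats the coding for the responder model.

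Protocol 9.4.2.1.1 states the order in words: the every-4-weeks arm is compared with placebo first, and the every-8-weeks arm only if that comparison succeeds. SAP 2 says "This version of the SAP is based on Amendment 3 of the Protocol", and SAP 12 declares no change to the testing order.

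**The concern.** The labels carry the confirmatory sequence. Under SAP 8.1, failure of the arm called Q4W stops testing of the arm called Q8W. Which regimen is the gatekeeper therefore depends on what Q4W means, and the SAP gives two answers: the glossary says one thing and 3.7 the opposite.

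Section 3.7 is the natural place to look, because it is the treatment-assignment section. The short forms beginning with Eto appear only there, in the 8.1.1.2 coding and in the 8.2.2 coding. A programmer who searches for the meaning of code 3 finds the identical string in 3.7, attached to the wrong regimen.

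Two things are at stake. One is the gate order at the final analysis. The other is which regimen each result is credited to, at both the final and the interim analysis. The interim (SAP 11.2) specifies no gate, so only attribution could go wrong there, but its results inform Phase 3 decisions.

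**Working it through.** No planned figure is in dispute, so the check is mainly a comparison of texts.

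**Step 1. Label against interval.** The interval is the gap between consecutive active-dose weeks listed in SAP 3.7.

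| SAP 3.7 arm | Active weeks | Gaps (weeks) | Glossary label | Label printed in 3.7 |
|---|---|---|---|---|
| Arm 1 | 0, 4, 8, 12 | 4, 4, 4 | Q4W | Q8W |
| Arm 2 | 0, 8 | 8 | Q8W | Q4W |

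Both active labels are crossed. Label and regimen are printed in full on both lines of current text, so neither extraction nor redaction explains the mismatch.

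**Step 2. Where the labels are used.** Outside the glossary and 3.7 there are six label-only uses: group labels (6.1), table columns (6.1), co-primary gate (8.1), treatment coding (8.1.1.2), secondary order (8.2) and responder coding (8.2.2). None restates the regimen.

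**Step 3. Effect on the gate.**

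| Meaning given to Q4W | Regimen tested first under SAP 8.1 | Agrees with Protocol 9.4.2.1.1? |
|---|---|---|
| SAP glossary or Protocol 10.3 | Every 4 weeks | Yes |
| SAP 3.7 as printed | Every 8 weeks | No, reversed |

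**Step 4. Size if 3.7 is followed.** SAP 3.6 plans about 33 subjects per arm: 27 / (1 − 0.18) = 32.9, rounded up to 33. Two active arms give 2 × 33 = 66 of 3 × 33 = 99 subjects reported under the other regimen's name. The power calculation uses the same n, difference and SD for each active arm against placebo, so it does not change with the labels. Alpha does not change either, because a fixed sequence controls it in either order.

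**Step 5. Would planned outputs reveal a swap?**
- *Exposure duration (SAP 10.1).* No. Both active arms have a Week 12 injection, which is placebo in the every-8-weeks arm. A fully dosed subject has (85 + 28) − 1 + 1 = 113 days in either arm.
- *Total drug administered and per-visit listing (SAP 10.1).* Yes, if they count etokimab separately from placebo. Active drug is scheduled at 4 visits in one arm and 2 in the other. With the load taken as the Week 0 dose, the totals are 300 + 3 × 150 = 750 mg against 300 + 1 × 150 = 450 mg. With the load taken as additional, they are 300 + 4 × 150 = 900 mg against 300 + 2 × 150 = 600 mg. The difference is 300 mg on either reading.
- *PK concentrations by arm (SAP 9.3.3).* Very likely. With the 14-day half-life in SAP 10.1 and a simple bolus assumption, a quarter of each dose remains after 4 weeks. With the load as the Week 0 dose, relative pre-dose amounts at Week 8 are 300/16 + 150/4 = 56.25 against 300/16 = 18.75, a ratio of 3.0. With the load as additional, they are 450/16 + 150/4 = 65.6 against 450/16 = 28.1, a ratio of 2.3. If labels were swapped, the column headed Q4W would show the lower concentrations.

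**The case against.** The strongest reply is that the text corrects itself. Each line in 3.7 prints the full interval next to the wrong label, so nobody reading it carefully would accept that Q8W means every 4 weeks. The glossary combined with SAP 3.4 gives a complete and correct mapping without 3.7. Protocol 9.4.2.1.1 states the order in words, and SAP 12 declares no departure from it. All of this stands, and it makes the intended order clear to a careful reader.

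Nor do the documents show a route from the 3.7 label to the data. Assignment comes from the IXRS treatment code and the randomization schedule, and the arm descriptors in those files are not visible here. This also stands: the reversed gate is a risk, not a demonstrated outcome. The dosing diagram in SAP 3.8 is not shown either and might carry labels, so the statement that 3.7 is the only section linking label and regimen is limited to the text available.

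Finally, a swap would probably be noticed. That holds for the final analysis, mainly through PK. The total-drug summary is a weaker safeguard, because the SAP does not say that it counts etokimab only. At the interim the protection is thinner: the items listed in SAP 11.2 include neither PK nor drug administered.

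These points limit the likely harm. They do not remove the contradiction, and a prespecified gate order should not depend on which SAP section a programmer consults.

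**Conclusion.** The labelling error is certain: both active-arm labels in SAP 3.7 are crossed. Its consequence is conditional. If programming follows the glossary or the Protocol, there is no effect. If it follows 3.7 as printed, the testing order of Protocol 9.4.2.1.1 is reversed for the co-primary and secondary endpoints, and two of three arms (about 66 of 99 planned subjects, assuming 33 per arm) are reported under the wrong regimen name. Alpha, stated power and sample size are the same in either case. The regimens themselves agree across both documents, so this is a labelling fault and not a dosing conflict. It should be corrected because the labels carry the gate and the correction costs almost nothing.

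**What to change.** In SAP 3.7, exchange the two parenthetical labels so that each agrees with the interval on its own line, the glossary, Protocol 10.3 and Protocol 9.4.2.1.1. Do this before the interim and final unblinded analyses.

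Two additions are optional. Add one line in SAP 8.1.1.2 tying treatment codes 2 and 3 to the regimen in words. Have the unblinded statistician confirm the mapping against the per-visit administration listing and the total-drug summary, counting etokimab and placebo separately. As a precaution, confirm that the separate DSMB SAP does not take its labels from 3.7.

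The cost is two labels and at most one further line of text. Design, data collection, alpha and sample size do not change.
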